## 9.6 Data Analyses

All outcome parameters for assessment of study feasibility are pass/fail criteria not requiring further analyses beyond calculations of sums and percentages.

To commit to a detailed analyses in Phase II, this can only be done with the proviso that the approach may change based on the data distribution, central measures and variation, and particularly time course, the determination of which is a goal of this Phase I trial.

For comparison of change in anxiety and pain from start to end of the waiting room time we propose t-test if normally distributed or the Mann-Whitney U test in the case of non-normal data.

For the time course assessment of pain and anxiety during the procedure there are options depending on whether the data meet the assumptions required for time course analysis.

Descriptive statistics (means and standard deviations as well as counts and percentages) will be calculated for each outcome stratified by time point and by

treatment group. Pain and anxiety trends over time will be assessed graphically for each patient stratified by treatment group.

With the provision that the analysis plan will be adapted based on the metrics found in Phase I, the plan is to follow a previously described path (24):

If the relationship between pain/anxiety is linear over time, and if needed, normality and homoscedasticity of residuals can be achieved by log-transformation, a repeated-measures analysis to compare the effect of treatment, time, and treatment by time interaction on pain and anxiety responses to characterize and compare trends in pain and anxiety ratings for the two treatment conditions over time (66, 67). The analysis will use the reports from the successive 10 min (+/- 2 mins) intervals queries obtained from all patients.

It may be that residuals are neither normally distributed nor possible to obtain a normal distribution by transformation. This happened in prior large scale trial with procedural pain procedural were 47% of pain responses were zero (45). To accommodate such a strong skew in reported pain, we would change our statistical approach to ordinal regression (68). If the proportional odds assumption is met, ordinal regression accounting for repeated measures will be performed to compare the effect of treatment, time, and interaction of treatment by time on pain and anxiety responses. The results will be presented in terms of the slopes of the time course of pain and anxiety on the logit scale.

If the data does not meet the assumptions required for the time-series analysis methods listed above, the time-series data from each patient will be summarized by calculating area under the curve using trapezoidal rule. Normality will be assessed graphically using histograms and q-q plots. Area under the curve will be compared between the two treatment groups using t-test if normally distributed or if normality can be achieved by log-transformation. Mann-Whitney U test will be used if data is non-normal.

Pain and anxiety for the week after the post procedure will be assessed for linearity graphically. Individual patient pain and anxiety slopes will be compared using t-test or Mann-Whitney U test, as appropriate, to determine if the rate of change of pain and anxiety is different between treatment and control groups. In addition, the overall mean pain and mean anxiety for each patient will be calculated and compared between treatment and control groups using t-test or Mann-Whitney U test as appropriate.

Drug usage, converted in equivalence drug score, and satisfaction scores will be assessed by t-test if normally distributed or Mann-Whitney-U test if non-normal.

All tests will be two-sided at a significance level of <0.05. Sample size will be based on results of Phase I assuming a power of 80%. SAS version 9.4 will be used for analysis.

Patients' age, gender, procedure type, and NIDA Quick score will be assessed for their potential as confounding factors. This will support guidance for trial design in Phase II.

The study sample of this pilot is likely underpowered to perform meaningful subanalyses of differences in intervention effect between gender and racial/ethnic subgroups. They will be performed to not miss potentially clinically significant differences as prescribed by NIH policy.

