#### 3. STUDY DESIGN

- 1. This is a single-blind placebo controlled trial comparing a Comfort Talk® calmative app (App Group) with a white noise app (Control Group).
- 2. Primary outcome parameter will be ability to obtain complete on-site data sets from at least 90% of patients enrolled (with at least 40% from patients in the app group and at least 40% from patients in the control group).

Secondary Feasibility parameters will be:

- ability to enroll 60 patients by day 150 after initiation of recruitment in the clinic
   (=day 1)
- obtaining 38 packages of filled out diary cards (at least 16 from patients in the app group and at least 16 from patients in the control group)
- 90% of patients in app group listen to app  $\geq 5$  min

Phase II outcome parameters:

Primary: anxiety at the end of the waiting room time.

Secondary:

- pain the end of the waiting room time
- anxiety during treatment
- pain during treatment
- anxiety during 1 week after treatment
- pain during 1 week after treatment
- use of units of sedatives and analgesics during 1 week after treatment
- patient satisfaction
- 3. Study population: 72 eligible patients (36 test group, 36 control group)

- 4. Study location: Outpatient clinic at TUSDM
- 5. Enrollment period and follow-up time:
  - For individual patients: time of clinic visit data collection on site plus 7 days at home follow-up by diary card
  - For the entire trial: 6 months
- 6. Description of intervention: The research assistant will hand the participant a tablet containing, depending on the group attribution, either the app (App Group) or white noise (Control Group) and will be shown how to operate the tablet.

Participant will then return to the clinic waiting area with the tablet and wait for their regularly scheduled appointment. The patient will be at liberty to when and for how long to listen.

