## 9.2 Sample Size and Randomization

The goal is to enroll 72 patients in a randomized design with 36 patients utilizing the app and 36 patients not utilizing the app. Those randomized to utilizing the app (app group) will receive a tablet with the app, those randomized to not utilizing the app (control group) will receive a tablet with white noise.

Based on prior trial experience, it is likely that 90% of patients on site will provide onsite data sets (primary objective). In two prior trials, in which 241 and 201 patients, respectively, were followed through their invasive medical procedures, all enrolled patients (100%) provided these data (1,3). In a breast-biopsy trial, 4 of 240 (1.6%) withdrew by that stage (2). In these past trials patients received more personal attention through live delivery of the content that is now offered in an app, and thus willingness to remain in the study may not be as high in the current trial but still should exceed 90% for feasibility. To arrive at a reasonable sample size to satisfy this requirement, but also obtain a sense of validity of the primary hypothesis for Phase II and obtain estimates of data distribution, which will be critical for sample size and analysis planning Phase II, we conducted following sample size calculations.

Assuming an average anxiety rating of 4 at the end of the waiting room time without prior guidance in relaxation or app (see Fig 3., time 0), the expectation of improved subsequent outcomes with a 35% reduction in anxiety to 2.6 based on Schupp et al (33 vs 53 on STAI - (1) and a standard deviation of 2, 66 patients would be needed for a two-sided test with a power of 0.80 and an alpha of 0.05.

This degree of reduction in anxiety is clinically significant based on prior work in a clinical trial that demonstrated that a 35% difference in anxiety at the onset of an invasive medical procedure is associated with significant differences in the subsequent experience of pain and anxiety during the procedure, need for opioid analgesics and sedatives, and the overall length of the procedure. These factors directly affect procedure safety and throughput (e.g. economical efficiency).

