Using this number of 66 patients as guide to determine a target study size for assessment of the feasibility parameters an enrollment of 72 patients seemed compatible with an early drop-out of 6 patients resulting in an expected 91.7% onsite data return rate. This will also support the expectation of receiving 38 packages of filled out diary cards (53%), a secondary objective. In a prior breast biopsy trial, in which patients collected for 5 days 4 daily salivary cortisol samples, filled out more extensive diary cards, and sent all back to the lab, 36% complied (45). Considering the higher burden of also getting 4 daily salivary samples and 4 daily entries as compared to one daily entry on cards at bed-time a 53% return rate for this pilot is reasonable.

This sample size of 72 participants may also give an estimate in as far results previously achieved with live delivery of Comfort Talk® may be transferable to assumptions for app delivered Comfort Talk® content.

The following sample size estimate supports the evaluation of post-procedure pain and is based on a prior breast biopsy trial (19) during which we collected postoperative pain measures. In that study, postoperative pain ratings in the live Comfort Talk group were less than those of the control group (1.6 vs 3.5) with a standard deviation of 2.0. Assuming a similar reduction in pain from 3.5 to 1.6 on day 1 (similar effect size in a study by from TUSDM) (43) and a standard deviation of 2.0, 38 subjects total would be needed for a two-sided test with a power of 0.80 and an alpha of 0.05. Considering that not everyone will send back their diaries, the target of 72 patients may suffice.

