#### 9.5.2 Secondary Outcomes

With regard to Phase I of the trial feasibility parameters will be

- number of enrolled patients by day 150 after initiation of recruitment in the clinic (=day 1)
- number of returned packages of filled out diary cards.
- percentage of patients in app group listen to app ≥5 min

With regard to Phase I

- anxiety on a validated 0-10 scale in the dental waiting room
- pain on a validated 0-10 scale in the dental waiting room
- anxiety q10 min (+/- 2 mins) on during dental treatment
- pain q10 min (+/- 2 mins) during dental treatment
- anxiety, average, and maximal anxiety for 7 days after treatment
- pain, average and maximal pain for 7 days after treatment
- use of prescription and nonprescription drugs for 7 days after treatment
- patient satisfaction

•

Pain and anxiety will be measured on 0-10 verbal self-reporting scales (0=no pain/anxiety at all, and 10=worst pain possible). The pain scale is recommended standard in the NIH Toolbox (62). For the 0-10 anxiety scale we previously demonstrated convergent and discriminant validity (63).

Anxiety and pain measures will obtained using these scales by verbally asking the patient "How is your Comfort Level on a scale with 0-no anxiety at all, and 10 worst anxiety possible and 0=no pain at all and 10=worst pain possible":

- At the beginning of the waiting room time after consent
- At the end of the waiting room time
- After the patient enters the dental treatment room and sits down = time 0 of chair time
- Every 10 minutes (+/- 2 minutes) thereafter while on the chair
- When leaving the dental treatment room

Once returned home the patients are asked to use the same scales to write down on daily diary cards for 7 days before bedtime as follows:

PLEASE INDICATE YOUR COMFORT LEVELS WITH A NUMBER BETWEEN 0 and 10

With regard to pain (0=no pain at all and 10=worst pain possible)

- Right now:
- On the average today:
- At its maximum today:

With regard to anxiety (0=no anxiety at all and 10=worst anxiety possible)

- Right now:
- On the average today:
- At its maximum today:

Patient Satisfaction will be assessed using a modified Press Ganey Outpatient Survey template (64) adjusted to dental care and supplemented with a question regarding helpfulness of the app on the same 5-point scale as the remainder of the survey. The Press Ganey instrument has been found to possess suitable psychometric properties for outpatient medical practice survey (65).

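### Phase II primary outcome and the 66-patient calculation use end-of-wait anxiety, but section 9.6 tests unadjusted change; ANCOVA on the baseline already collected would match the outcome and be more precise

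*Combined protocol and SAP*

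**What the plan says.** - **Outcome.** Section 3 gives the Phase II outcome as "Primary: anxiety at the end of the waiting room time". The Précis says the same. This is a level at one time point, not a change.
- **Sample size.** Section 9.2 works from the same level: "Assuming an average anxiety rating of 4 at the end of the waiting room time without prior guidance in relaxation or app", falling by 35% to 2.6, with an SD of 2, two-sided alpha 0.05 and 80% power. The result is 66 patients. Its role is limited: "Using this number of 66 patients as guide to determine a target study size for assessment of the feasibility parameters", leading to an enrolment of 72.
- **Analysis.** For the change in anxiety and pain between the start and end of the wait, section 9.6 says "we propose t-test if normally distributed or the Mann-Whitney U test in the case of non-normal data". No covariate is named.
- **Baseline.** Section 9.5.2 schedules a rating on the same 0-10 scale "At the beginning of the waiting room time after consent", and section 6.2.2 lists it among the baseline assessments.
- **Covariates considered.** Section 9.6 says that "age, gender, procedure type, and NIDA Quick score will be assessed for their potential as confounding factors". The baseline rating is not in that list.
- **What the pilot reports.** Means, SDs, counts and percentages "will be calculated for each outcome stratified by time point and by" treatment group.
- **Use of the results.** Section 9.6: "Sample size will be based on results of Phase I assuming a power of 80"%.

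**The concern.** The stated outcome and the power calculation concern the end value, while the proposed test concerns the change. The expected difference between arms is the same for both under randomization, but the SD is not. The SD of a change depends on the baseline SD and on rho, and the documents give neither. The 80% power was calculated for the end value and carries over to the change score only if rho is high enough.

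The change score also makes restricted use of the baseline. It fixes the slope of the end value on the baseline at 1, whereas ANCOVA estimates that slope from the data.

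What is at stake is mainly Phase II. If Phase II is sized on one variance and analysed with a test that has another, it will be too small or larger than it needs to be. Summaries by time point and group do not supply rho or the ANCOVA residual SD, although the paired ratings allow both to be computed.

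**Working it through.** **Inputs from the documents.** Section 9.2: means 4 and 2.6, so a difference of 1.4; SD 2; two-sided alpha 0.05; power 0.80; 36 + 36 enrolled, with 6 early drop-outs, which leaves 66 (33 per arm).

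**Assumptions, not in the documents.** Baseline SD s0 = 2 (varied from 1.5 to 2.5); rho = 0.3, 0.5 or 0.7; normally distributed ratings.

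**Step 1: reproduce the 66.** By the normal approximation, n per arm = 2 × (1.960 + 0.842)² × 2² / 1.4² = 32.04, rounded up to 33, so 66 in total. The noncentral t gives 33.02 per arm and 79.97% power at 33. The stated figure reproduces as an unadjusted comparison of end values.

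**Step 2: the SD for each test.**
- End value: 2.
- Change score: √(2² + s0² − 2·rho·2·s0) = √(4 + s0² − 4·rho·s0). With s0 = 2 this is 2√(2(1 − rho)).
- ANCOVA residual: 2√(1 − rho²), which does not depend on s0.

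With s0 = 2, the ratio of ANCOVA to change-score variance is (1 − rho²) / (2(1 − rho)) = (1 + rho)/2, which is below 1 for every rho below 1.

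**Step 3: power with 33 per arm** (noncentral t; 64 degrees of freedom, 63 for ANCOVA; s0 = 2).

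| rho | SD of change | ANCOVA residual SD | End value | Change score | ANCOVA |
|---|---|---|---|---|---|
| 0.3 | 2.366 | 1.908 | 80% | 66% | 84% |
| 0.5 | 2.000 | 1.732 | 80% | 80% | 90% |
| 0.7 | 1.549 | 1.428 | 80% | 95% | 98% |

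A simulation of 20,000 bivariate normal trials per setting gives 66%, 81% and 95% for the change score and 83%, 90% and 97% for ANCOVA. If all 72 are analysed, the change score has 70%, 83% and 97%, and ANCOVA 87%, 92% and 98%. At rho 0 with 66 patients, ANCOVA still has about 79-80%.

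**Step 4: the rho at which the change score keeps its power.** With 66 patients the SD of change must be no more than 2. Setting 4 + s0² − 4·rho·s0 = 4 gives rho = s0/4. With 72 patients the SD of change may be as large as 2.09.

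| Baseline SD | Minimum rho, 66 patients | Minimum rho, 72 patients |
|---|---|---|
| 1.5 | 0.38 | 0.31 |
| 2.0 | 0.50 | 0.45 |
| 2.5 | 0.63 | 0.59 |

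At rho 0.5 and 33 per arm, change-score power is 87% with s0 = 1.5 and 69% with s0 = 2.5.

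**Step 5: total N for 80% power** (s0 = 2).

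| rho | Change score | ANCOVA |
|---|---|---|
| 0.3 | 92 | 62 |
| 0.5 | 66 | 52 |
| 0.7 | 42 | 36 |

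These are the smallest even totals that reach 80%, except that 66 follows the protocol's own rounding (79.97%). The normal approximation gives totals up to 2 lower.

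**The case against.** The strongest reply is that nothing in this trial turns on the test. The feasibility outcomes are pass/fail counts and percentages, the 66 is only a guide, and section 9.6 says expressly that the Phase II approach may change once the pilot has shown the distribution, variation and time course. All of that stands. It limits the severity and rules out any claim that the pilot is invalid.

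A second reply is that a change score is a reasonable test of the section 9.1 hypothesis that the app lowers waiting-room anxiety, and that it targets the same expected difference of 1.4. That is also true. The mismatch lies in the variable analysed and its SD, not in the treatment effect. An unadjusted test of the end value would remove the inconsistency too; ANCOVA is preferred because it is also more precise.

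A third reply is that rho may well exceed 0.5, since the two ratings use the same scale in one visit about half an hour apart. At rho 0.8 with equal SDs, the change score has 99.3% power and ANCOVA 99.7%, so the gain is negligible. This is plausible but unknown. ANCOVA does well across the whole range, and the change score does not.

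Two further points are fair. A t-test on change computes the SD of change in passing, and the other quantities can be obtained later from the retained data. The figures here also assume normality, so no gain has been shown for a rank-based or ordinal version, or for pain.

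The proviso in section 9.6 does not mention baseline adjustment, so an explicit instruction still adds something.

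**Conclusion.** The concern holds, as a matter of precision and consistency. The outcome and the sample size use the end-of-wait value, the proposed test uses unadjusted change, and a same-scale baseline is collected without being used as a covariate. The 66 is arithmetically correct for what it calculates, and the change-score test is not biased.

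Under equal SDs of 2, the change score falls short of the planned 80% with 66 patients whenever rho is below about 0.50. At rho 0.3 it has 66% power where ANCOVA has 84%, and it would need 92 patients against 62. At rho 0.7 the power gap narrows to 95% against 98%. These sizes rest on assumed values of rho and the baseline SD. The consequence falls on the sizing and analysis of Phase II, not on the feasibility result. The change is worth making because it costs almost nothing.

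**What to change.** In section 9.6:

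1. Analyse end-of-waiting-room anxiety, and separately pain, by ANCOVA with treatment arm and the pre-intervention rating of the same scale as terms. If residuals are clearly non-normal, use a rank-based or ordinal model with the same covariate.
2. Add to the descriptive statistics the baseline-to-end correlation, the SD of change and the ANCOVA residual SD.
3. State that Phase II will be sized on the variance belonging to the test it will use.
4. Optionally, add the same baseline covariate to the in-chair and diary comparisons. No gain has been quantified for those.

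The cost is a change of wording in the analysis plan. It needs no new data, visits or patients.

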## **Design and Outcomes**

The design is a single-blind, placebo controlled clinical trial to test the feasibility of the trial design assessing the ability of a Comfort Talk® app to nonpharmacologically reduce anxiety, pain, and periprocedural drug use in individuals 18 years of age and older undergoing outpatient treatment in the Craniofacial Pain Center of the Tufts School of Dental Medicine.

The trial is a single-site pilot trial to assist in sample size estimation in a pivotal trial to test the hypothesis that listening to a Comfort Talk® app with calmative content reduces pain, anxiety, and post-procedural medication use.

Eligible patients at the Craniofacial Pain Center at the Tufts School of Dental Medicine (TUSDM) will be randomized to listen to a tablet containing a calmative Comfort Talk® app or app with white noise on an intent-to-treat basis. Their anxiety and pain measures will be recorded on validated 0-10 scales and before listening, at the end of the waiting room period, and every 10 minutes (+/- 2 minutes) while on the dental chair.

All patients will be given a packet with diary cards to record their levels of anxiety, pain, and drug use daily for 7 days after their visit and asked to send those back. Subjects will be mailed a \$25 check upon returning their diaries.

Patients randomized to the Comfort Talk® app will receive a download coupon for the app before leaving TUSDM, those randomized to the control condition (white noise) will receive a download coupon after they send in their diary cards.

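### The during-treatment pain and anxiety analyses in 9.6 leave out each patient's pre-listening rating, which costs precision for the treatment (level) contrast and for AUC, though not for the slope

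*Combined protocol and SAP*

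**What the plan says.** Section 9.6 sets out three routes for pain and anxiety during treatment.

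- If the course is linear and the residuals behave, the plan is "a repeated-measures analysis to compare the effect of treatment, time, and treatment by time interaction on pain and anxiety responses". The data are the chair ratings: "The analysis will use the reports from the successive 10 min (+/- 2 mins) intervals queries obtained from all patients".
- If the residuals cannot be made normal and proportional odds holds, "ordinal regression accounting for repeated measures will be performed to compare the effect of treatment, time, and interaction of treatment by time".
- If neither set of assumptions is met, each patient's series is reduced to a trapezoidal AUC. "Area under the curve will be compared between the two treatment groups using t-test if normally distributed", with log-transformation allowed and Mann-Whitney for non-normal data.

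A baseline rating exists. Section 9.5.2 lists the first rating as taken "At the beginning of the waiting room time after consent", and the Précis (Design and Outcomes) has ratings "recorded on validated 0-10 scales and before listening, at the end of the waiting room period". Section 6.2.2 places randomization after baseline, and section 6.2.5 has the tablet handed over once baseline data are in hand.

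In 9.6 that rating is used only for the waiting room, where the change from start to end is compared: "we propose t-test if normally distributed or the Mann-Whitney U test in the case of non-normal data". The factors marked for assessment do not include it: "Patients' age, gender, procedure type, and NIDA Quick score will be assessed for their potential as confounding factors".

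**The concern.** The treatment term in a repeated-measures model compares different patients. Modelling the correlation among one patient's ratings gives a correct standard error, but it does not remove the variation between patients that was there before the tablet was handed over. The population is drawn from a craniofacial pain clinic with procedures from appliance fitting to nerve blocks, so starting levels probably differ a good deal. The third premise in section 2.2 says that anxiety just before a procedure predicts anxiety and pain during it.

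A covariate that is measured before exposure, on the same scale and in every patient, is therefore available but unused. Two of the eight Phase II hypotheses in 9.1 (anxiety and pain during dental treatment) are addressed by these analyses. What is at stake is the precision of those two estimates.

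**Working it through.** **The plan's own figure.** Section 9.2 assumes waiting-room anxiety of 4 against 2.6 (difference 1.4), SD 2, two-sided alpha 0.05 and power 0.80. The normal formula gives n per arm = 2 × (1.960 + 0.842)² × 2² / 1.4² = 32.04, rounded up to 33, or 66 in total. This matches the stated 66. The noncentral t gives power 0.800 at 33 per arm. The plan states no power for during-treatment outcomes.

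**Inputs for the chair ratings.**
- 33 per arm: 72 enrolled less the 6 early drop-outs allowed for in 9.2.
- SD 2: borrowed from the waiting-room calculation.
- Four ratings: an average 45-minute procedure rated every 10 minutes, not counting time 0.
- Within-patient correlation among chair ratings 0.6: assumed.
- Correlation ρ of the pre-listening rating with each chair rating: assumed, 0.3 or 0.5. A value above 0.6 would exceed the assumed correlation between the chair ratings themselves.
- Difference 1.0 point, with 1.4 alongside: assumed.

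**Level contrast, mean of four ratings.**
Unadjusted variance = 4 × (0.6 + 0.4/4) = 2.80, SD 1.673.
Correlation of baseline with the mean, r = ρ × 2/√2.80, which is 0.359 (ρ 0.3) or 0.598 (ρ 0.5).
Adjusted variance = 2.80 × (1 − r²) = 2.80 − 4ρ².
Standard error = SD × √(2/33) = SD × 0.246.

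| | Variance | SD | SE | Power, 1.0 point | Power, 1.4 points |
|---|---|---|---|---|---|
| Unadjusted | 2.80 | 1.673 | 0.412 | 0.667 | 0.917 |
| Adjusted, ρ 0.3 | 2.44 (−13%) | 1.562 | 0.385 | 0.726 | 0.948 |
| Adjusted, ρ 0.5 | 1.80 (−36%) | 1.342 | 0.330 | 0.846 | 0.987 |

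Power is from the noncentral t with 64 degrees of freedom unadjusted and 63 adjusted.

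**AUC.** Divided by its duration, the trapezoidal AUC of four ratings is a weighted mean with weights 1/6, 1/3, 1/3, 1/6, whose squares sum to 0.278. Variance = 4 × (0.6 + 0.4 × 0.278) = 2.84. Subtracting 4ρ² leaves 2.48 (−13%) at ρ 0.3 or 1.84 (−35%) at ρ 0.5. The gain is essentially that of the mean.

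**A second correlation structure.** With five chair ratings (0 to 40 minutes) and one common correlation ρ among all ratings including baseline, adjustment multiplies the variance of the level contrast by 0.80, 0.58 or 0.36 for ρ of 0.3, 0.5 or 0.7.

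**Slope.** The weights that form a patient's least-squares slope sum to zero. If the baseline rating is equally correlated with every chair rating, its covariance with the slope is therefore zero, and adjusting for it removes nothing. In the five-rating calculation the standard error of the treatment-by-time contrast is the same with and without baseline: 0.130, 0.110 and 0.085 per 10 minutes for ρ of 0.3, 0.5 and 0.7. A gain would need a baseline correlation that drifts over chair time.

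**The case against.** The strongest reply is that 9.6 describes a time-course analysis. It compares trends and presents the ordinal results as slopes, and for slopes the gain vanishes. That stands, and it confines the point to the treatment term and AUC. It does not remove the point: the treatment effect is named in both models, AUC is a level measure, and the hypotheses in 9.1 about reduced anxiety and pain during treatment read naturally as claims about level.

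Three stronger readings are tempting, and the documents do not support them.

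- A reader might infer that chance imbalance makes the unadjusted treatment effect biased. Allocation is randomized, so the unadjusted tests remain valid; what is lost is precision. In the ordinal model the adjusted and unadjusted odds ratios also measure slightly different things, the unadjusted one lying nearer to one, but the unadjusted test is still valid.
- A reader might infer that Phase II will be sized on an inflated variance. The Phase II primary outcome is anxiety at the end of the waiting time, which these models do not analyze, and 9.6 does not say that sizing will use chair ratings.
- A reader might infer a defect in the trial's main result. The primary outcome is the percentage of complete on-site data sets, which is unaffected. No power is claimed for during-treatment outcomes.

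It is also fair to say that 9.6 is expressly provisional, and that it follows a published analysis which cannot be consulted here and may have had further terms. But the proviso ties changes to distribution and time course, and nothing in the text commits to baseline adjustment. Finally, the calculations above are normal-theory, whereas 9.6 anticipates that many pain ratings may be zero; no figure for the ordinal model is available.

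**Conclusion.** The omission is real in both models and in the AUC fallback, and no other section supplies the adjustment. The consequence is a loss of efficiency, without bias, for the treatment (level) contrast and for AUC. The treatment-by-time slope gains little or nothing.

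For a 1.0-point difference, about 6 points of power are lost at a baseline correlation of 0.3 and 18 points at 0.5; for 1.4 points the losses are about 3 and 7. These figures rest on a borrowed SD and sample size, and on correlations and differences that the documents do not give. The direction is firmer than the size. The protocol's rationale supports the prognostic value of anxiety; for baseline pain it is a reasonable expectation that the documents do not state. This is an inexpensive improvement to secondary, provisional analyses.

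**What to change.** In 9.6:

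1. Add the pre-listening rating of the same measure (pain for pain, anxiety for anxiety) as a prespecified covariate in the repeated-measures and ordinal models.
2. Replace the AUC t-test with a linear model of AUC on treatment and that rating.
3. Where AUC is non-normal, replace Mann-Whitney with a covariate-adjusted rank method, for example rank ANCOVA.
4. State that the covariate is the pre-listening rating. The end-of-wait and chair time 0 ratings follow randomization and the chance to listen, so adjusting for them could remove part of the app's effect.
5. Report the baseline correlation and the adjusted residual SD as information for planning the Phase II secondary outcomes.

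The cost is one degree of freedom per model. The ratings are already collected, so no new data and no change in study conduct are needed.
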